Since there are several endpoints in this study, the required sample size can be calculated in several ways:

-Using efficacy as an endpoint:

In Janis *et al*,⁶ patients undergoing botulinum toxin injections had an average improvement in their Migraine Headache Index of 87.5%. In comparison, patients undergoing surgery had an average improvement of 96.6%.

Assuming a standard deviation of 20%, an alpha error of 5%, and a power of 80%, the required sample size using this method is **30 patients in each group**.

-Using total cost of treatment as an endpoint:

Assuming an average injection volume of 75 Units of botulinum toxin every 3 months, and assuming a cost of \$12-15 per Unit, the estimated cost of a botulinum toxin A injection protocol over one year is \$3,600-\$4,500.

In comparison, the estimated cost of surgery (including facility fee, surgeon fee, preoperative testing and follow-up) is \$8,378.¹⁰

Therefore, in order to demonstrate a financial superiority of surgery versus botulinum toxin, the patients would need to be follow-up for 1.9 to 2.3 years. Assuming a study follow-up of 2.5 years, and average costs of botulinum and surgery of $$10,125 \pm $2,000$ and $$8,378 \pm $2,000$, respectively, and assuming an alpha error of 5%, a power of 80%, the required sample size using this method is **16 patients in each group**.

-Using treatment success by trigger site as an endpoint:

According to Larson *et al*,⁹ the success rates for surgery by trigger site were as follows: Frontal 83.3%, temporal 75.8%, and occipital 45.5%. In order to discern a difference between the outcomes for the two sites with the closest outcomes (frontal and temporal), and assuming a standard deviation of 10%, an alpha error of 5%, and a power of 80%, the required sample size using this method is **14 patients in each group**.

Looking at the three methods above, keeping the method yielding the highest required number of participants, and accounting for any participant drop-out, we will seek to enroll **50 patients in each group.**

c. Detailed study procedures

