50 patients who prefer surgery, and who satisfy the inclusion and exclusion criteria, will be included in the study as **Group A**. The location of the trigger site(s) will be determined based on history, physical examination, a diagnostic botulinum toxin injection and/or a nerve block. If those patients are found to have a trigger site that responds to botulinum injection, they will undergo surgical decompression of their trigger site, as described in Janis *et al*⁶ and Guyuron *et al*.⁷ Those patients will be followed postoperatively. They will be asked to continue tracking their 1) daily use of medications for migraines, 2) physician visits for migraines, 3) ER visits for migraines, 4) days of work lost due to migraines, and 5) other costs directly related to migraines for 2 months. At 1 year, 2 years and 2.5 years postoperatively, they will be asked to fill the Migraine Work and Productivity Loss Questionnaire (MWPLQ), the Migraine Disability Assessment questionnaire (MIDAS) and the Migraine-Specific Quality of Life questionnaire (MSQ) again. They will also be examined by a board-certified neurologist at 1 year postoperatively.

A separate sample of 50 patients from the pool of patients undergoing the botulinum toxin injection protocol will be selected (Group B). Those patients will be matched to the individual patients in group A based on gender, age (in 5 year intervals), migraine severity (based on the Migraine Disability Assessment questionnaire, 5 –point intervals) and trigger site (pair-matching). For example, for a patient in Group A who is a 47 year-old woman with temporal migraines and a MIDAS severity score of 14, a patient on the botulinum injection protocol will be included in Group B is she is a 45 to 50 year old female with temporal migraines and a MIDAS severity score of 10 to 15.

The patients in group B will receive the botulinum injection protocol, and will continue to track their 1) daily use of medications for migraines, 2) physician visits for migraines, 3) ER visits for migraines, 4) days of work lost due to migraines, and 5) other costs directly related to migraines for 2 months. At 1 year, 2 years and 2.5 years after the start of the protocol, they will be asked to fill the Migraine Work and Productivity Loss Questionnaire (MWPLQ), the Migraine Disability Assessment questionnaire (MIDAS)

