and the Migraine-Specific Quality of Life questionnaire (MSQ). They will also be examined by a board-certified neurologist at 1 year postoperatively.

The Botox injections and the surgeries are being done as part of the routine clinical care for the patients enrolled in the study. The only procedures being done solely for research purposes are having the patients fill out the surveys and diaries.

d. Measurements

The measurements will include

- 1) Number of migraine headaches per 30 days
- 2) Cost of migraine-related medications, physician visits, ER visits
- 3) Cost of days of work lost due to migraine as calculated from the Migraine Work and Productivity Loss Questionnaire (MWPLQ)
- Score on the Migraine Disability Assessment Questionnaire (MIDAS) (0-21)
- 5) Scores on the emotional, restrictive and preventive portions of the Migraine-Specific Quality of Life questionnaire (MSQ)

The following comparisons will be made for the above measurements:

-Within Group A, compare all measurements before surgery to 1 year, 2 years and 2.5 years after surgery, using a t-test

-Within Group B, compare all measurements before start of injection protocol to 1 year, 2 years and 2.5 years after injection protocol, using a t-test

-Compare all measurements between Group A and Group B using a paired t-test analysis

e. Internal validity

The study avoids confounding by virtue of the matched-pair analysis. The study avoids recall bias by having the patients fill-out the questionnaires preoperatively and postoperatively, rather than having them retrospectively assess their improvement after surgery.

Blinding is very difficult in such a study. In order to avoid experimenter bias, all assessment will be made by the patients themselves, without influence by the experimenters.

The main threat to internal validity is the possible placebo effect inherent to migraine headache treatments. This may threaten the validity of the data on differences in clinical outcomes between the two groups. It will not threaten the validity of the data on financial cost

f. External validity

Because this is a multi-center trial that includes different patient populations treated by different clinicians, this study is generalizable to the general population of patients with migraines in the United States.

g. Data analysis

Group B will be selected by matching individual participants to members of Group A based on gender, age, migraine severity and migraine location.

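### The planning cost is drug only for botulinum but a bundle for surgery, so the break-even is not like for like, and the measurement list names no procedure cost for either treatment

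*Protocol*

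**What the plan says.** **Planning figures (Protocol III.b, Sample size, total cost endpoint).** Botulinum is costed from "Assuming an average injection volume of 75 Units of botulinum toxin every 3 months" and a price of $12–15 per Unit, giving $3,600–$4,500 a year. Surgery is costed from a cited source at $8,378, described as "the estimated cost of surgery (including facility fee, surgeon fee, preoperative testing and follow-up) is" that amount. The protocol concludes that "the patients would need to be follow-up for 1.9 to 2.3 years" before surgery is financially superior. It then continues "Assuming a study follow-up of 2.5 years" and plans on $10,125 against $8,378, with an SD of $2,000 in each arm and 16 patients per group.

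**Diagnostic botulinum.** For Group A, III.c states: "If those patients are found to have a trigger site that responds to botulinum injection, they will undergo surgical decompression". The exclusion criteria in III.b remove patients whose trigger point does not respond to a diagnostic injection, and do not limit this to Group A. III.c describes trigger-site determination for all patients.

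**What is measured (III.d).** Measurement 2 reads "Cost of migraine-related medications, physician visits, ER visits". Measurement 3 is the cost of lost work. III.c also has both groups track other migraine-related costs for 2 months, but these do not appear in the list of measurements. The SAP models six outcomes, and none is a cost.

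**The concern.** Objective 4 is a comparison of long-run direct and indirect costs, with the hypothesis that surgery is the more cost-efficient. Such a comparison means something only if both arms are charged for the same kinds of item. In the planning figures one arm carries drug alone, while the other carries professional, facility, testing and follow-up charges. The measurement list does not repair this. Followed as written, it names neither the cost of the operation nor the cost of giving the injections. The protocol's section on internal validity also presents the cost data as the part that a placebo effect does not threaten, so their construction deserves care.

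**Working it through.** **1. Reproduce the plan's figures.** Inputs are from III.b: 75 Units, 4 sessions a year, $12–15 per Unit, surgery $8,378.

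- Annual botulinum cost: 75 × 4 × $12 = $3,600 and 75 × 4 × $15 = $4,500. Both match to the dollar, so nothing but drug is included.
- Break-even = surgery cost ÷ annual botulinum cost: 8,378 ÷ 4,500 = 1.86 years and 8,378 ÷ 3,600 = 2.33 years. The stated 1.9–2.3 reproduces.
- Botulinum over 2.5 years at the mid price: 2.5 × $4,050 = $10,125. Difference: 10,125 − 8,378 = $1,747.

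The arithmetic is sound. The fault lies in what is counted.

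**2. Add an administration fee to botulinum.** The documents give no fee, so assume f = $50–500 per session. Break-even = 8,378 ÷ [4 × (75p + f)], with p the unit price. Over 2.5 years there are 10 sessions, so the difference is 1,747 + 10f.

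| f | Break-even (p = $15, $12) | Difference at 2.5 years |
|---|---|---|
| $50 | 1.78, 2.20 years | $2,247 |
| $100 | 1.71, 2.09 years | $2,747 |
| $200 | 1.58, 1.90 years | $3,747 |
| $500 | 1.29, 1.50 years | $6,747 |

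**3. Charge one diagnostic injection to surgery only, with no fee.** The documents give no diagnostic dose. The 25–75 Units used here are a costing assumption only. Break-even = (8,378 + u·p) ÷ (300p). Difference = 1,747 − 13.5u.

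| u | Break-even (p = $15, $12) | Difference at 2.5 years |
|---|---|---|
| 25 Units | 1.95, 2.41 years | $1,409.50 |
| 50 Units | 2.03, 2.49 years | $1,072.00 |
| 75 Units | 2.11, 2.58 years | $734.50 |

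**4. Combine the two, with a 75 Unit diagnostic session that also carries the fee.** Botulinum = 10,125 + 10f. Surgery = 8,378 + 1,012.50 + f. The difference is 734.50 + 9f, which returns to $1,747 when f = 1,012.50 ÷ 9 = $112.50. Break-even is then 1.94–2.32 years, almost as stated.

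**5. Charge the diagnostic injection to both groups.** It cancels, and break-even stays at 1.86–2.33 years.

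**6. Bearing on sample size.** The three calculations in III.b give 30, 16 and 14 per group. The largest, from efficacy, is carried forward to the target of 50. The cost calculation does not set enrolment.

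**The case against.** The strongest reply has four parts.

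- **The one proven omission is conservative.** Leaving out an injection fee understates botulinum cost and so works against the sponsor's own hypothesis. Correcting it alone shortens break-even and widens the difference. This stands.
- **The diagnostic injection may not be missing.** It could sit within the testing component of the $8,378, whose source cannot be checked here. If Group B has it too, it cancels. This also stands. A reader might infer that the injection was left out and is a Group A cost only, but the documents establish neither.
- **A planning assumption does not bias observed costs.** That is true. Both groups also track the same categories, including other migraine-related costs, and botulinum drug and injection visits might be recorded as medication and physician visits. But the tracking of other costs is stated for 2 months and is not among the listed measurements, and no listed item names the operation. Identical tracking therefore does not show that total treatment cost is captured.
- **The design consequence is small.** Enrolment rests on efficacy, and the SAP models no cost. The first fact limits the harm. The second leaves Objective 4 without any definition of total cost elsewhere.

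**Conclusion.** The mismatch is established from III.b alone: drug units times price in one arm, a four-item bundle in the other. The 1.9–2.3 year break-even and the $1,747 difference are therefore not like for like, although correctly calculated. The measurement list separately fails to name surgery and injection procedure costs.

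The size and direction of the net error cannot be determined. Under the assumptions above, break-even could fall to 1.3 years, rise to 2.6 years, or hardly move.

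A reader might go further and infer that surgery cannot break even within follow-up, or that the cost comparison is underpowered. At 75 Units and $12, surgery would be 8,378 + 900 = $9,278 against $9,000 for botulinum at 2.5 years. At the mid-price difference of $734.50, two-sided power with 50 independent patients per group is about 45%: 734.50 ÷ (2,000 × √(2/50)) = 1.84, less 1.96. Both results need a 75 Unit diagnostic dose, charged to Group A only, with no injection fee; the first also needs the lowest unit price. The documents do not support that combination over the others.

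Nor do they say that the 2.5-year horizon was chosen from the break-even. The adjoining sentences suggest it, but it remains an inference.

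**What to change.** - **Define total cost once, for both arms, from enrolment to 2.5 years.** Include all botulinum drug, diagnostic and therapeutic; all procedure, facility and professional fees; and migraine medication, visit, ER and lost-work costs.
- **Add the missing components to measurement 2**, taken from billing records, and carry the same definition into the SAP.
- **State two facts:** whether the $8,378 includes diagnostic botulinum, and whether Group B also receives it.
- **Restate the break-even and the planning difference** on that basis, with a range where a fee or quantity is assumed.

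The cost is protocol and SAP wording plus some work on billing data. III.c says that injections and surgery are routine care, so these items should already exist. No clinical procedure changes. The downside is that the planning difference may become less favourable to surgery.

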Similarly, surgical decompression of trigger sites has previously been shown to have superior clinical outcomes to medical management, through a randomized, blinded controlled-trial performed at Case Western Reserve in 2009.⁷ Patients either received actual decompression of the trigger sites, or sham surgery (exposure and visualization of the trigger sites, without decompression). At one-year follow-up, the group who underwent actual surgery demonstrated a statistically higher proportion with significant improvement in their migraines (83.7% vs. 57.7%, p=0.014), and with complete elimination of their migraines (57.1% vs. 3.8%, p<0.001). Several other reports have confirmed the good clinical outcomes of surgery demonstrated in this trial,^{6,8} and surgical decompression is now commonly performed by several surgeons around the United States.

Prognostic factors predicting the success of surgical decompression in migraine headache treatment include older age of migraine onset, visual symptoms/aura, and 4-site decompression. Factors predicting failure of surgery include excessive operative blood loss, and surgery on only one or two trigger sites.⁹

One criticism of the studies on migraine surgery has been that most of the results have originated from the same institution (Case Western Reserve), and from the same author (Guyuron). While several studies at other institutions have demonstrated positive outcomes of migraine surgery,⁶ these have only included a small number of patients.

In addition, the sham surgery randomized-controlled trial has been criticized for not clarifying any prior treatments that patients had undergone before migraine surgery, and for not showing how medication use patterns changed after surgery. Another criticism of that study was the fact that patients were examined by neurologists before the study but not after the study, and that surgery was performed on some patients with episodic migraines, who are known to not benefit from botulinum toxin. It is unclear what migraine types are most likely to benefit from surgical decompression.

Our goal is to perform a multi-center, prospective trial to demonstrate the effectiveness of migraine surgery, which would address the criticisms mentioned above. The main aim is to demonstrate that the positive results demonstrated by Guyuron *et al* are reproducible at other institutions and by other surgeons using similar techniques on different patient populations.

II. Objectives

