Prospective, Multi-Center Evaluation of the Efficacy of Migraine Surgery

Statistical Analysis Plan

IRB Approval #:2015H0024

NCT02351544

Document Date Version: February 16, 2014

Principal Investigator: [name], FACS (The Ohio State University)

Outcomes

**Outcomes modeled were: MHI, MIDAS A, MIDAS B, MIDAS Total, MSQ Sum and MWPLQ7 Total

Data Analysis

Descriptive statistics, such as frequency and percents, were displayed for sex (male or female), treatment (Botox or Surgery) and site (OSU or MGH). Descriptive statistics, such as mean, standard deviation, median, lower quartile and upper quartile, were reported for age and the patient reported outcomes with the respect to their migraine for each time point (baseline, 1 year, 2 years and 2.5 years).

Each of six outcomes were highly skewed and therefore natural logarithm was applied to each one before it was modeled. A constant of 1 was added to outcome values before applying natural log function so as to include raw values of zeros.

Linear mixed models with a random effect for patient were used to evaluate the changes in each of six outcomes between two different treatments over time with inclusion of interaction between treatment and time. These models were used given to account for correlation between repeated measurements on the same patient and to account for missing data across time points. P-values for both the main and interaction effects of time and treatment were reported for each model and Tukey's post hoc method was used to adjust for pairwise comparisons. For the ease of interpretation, raw means and SDs are presented for each time point within specific treatment.

Analyses were performed using SAS v9.4 (SAS Institute; Cary, NC; www.sas.com). Statistical significance was defined as two-sided alpha<0.05.

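### The trigger-site sample size of 14 is per site among surgical patients, yet it is ranked against per-arm figures without conversion, so 50 surgical patients may not secure it

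*Protocol*

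**What the plan says.** Protocol III.b (Sample size) works through three endpoints. Efficacy and total cost each compare surgery with botulinum toxin and give 30 and 16 per group, so a group there is a treatment arm.

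The third endpoint is treatment success by trigger site. Its inputs come from operated patients only: "the success rates for surgery by trigger site were as follows: Frontal 83.3%, temporal 75.8%, and occipital 45.5" percent. The contrast is set out as "In order to discern a difference between the outcomes for the two sites with the closest outcomes (frontal and temporal"), "assuming a standard deviation of 10%, an alpha error of 5%, and a power of 80" percent, and the result is "14 patients in each group". Here a group can only be a trigger site.

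The section then combines the three: "Looking at the three methods above, keeping the method yielding the highest required number of participants", allows for drop-out at an unstated rate, and arrives at 50 per group.

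III.c defines Group A as 50 eligible patients who prefer surgery. It sets no minimum or expected number per site. Of patients whose site responds to botulinum toxin it says "they will undergo surgical decompression of their trigger site", in the singular, but the sentence on locating triggers allows for more than one site per patient. Group B is matched to Group A on trigger site and is not operated on as part of the plan.

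**The concern.** Taking the largest of 30, 16 and 14 makes sense only if all three count the same thing. Two count patients per arm and one counts patients per site within one arm. Group B cannot make up a shortfall, because the success rates being compared are those of surgery.

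The 50 per arm is therefore offered as covering an endpoint that was never converted to a per-arm requirement. Prognostic factors for surgical success are a stated objective (Protocol II, item 3), and trigger site is the only such factor that III.b sizes. If frontal and temporal results are later compared and no difference is found, a reader of III.b could take that as evidence of similar outcomes, when the site groups may have been too small to show one.

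**Working it through.** **Inputs.** From Protocol III.b: frontal 83.3%, temporal 75.8%, SD 10 points, alpha 5%, power 80%, stated n = 14. The difference is 83.3 − 75.8 = 7.5 points. III.b does not state sidedness; the SAP says "Statistical significance was defined as two-sided alpha<0.05", so two-sided is used. Eligible sites (III.b, inclusion criteria): frontal, temporal, occipital. Not in the documents, and so assumed: the site mix, the drop-out rate, and one site per patient.

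**1. Reproducing the 14.** (1.96 + 0.842)² × 10² / 7.5² = 13.95, which rounds up to 14. This is the formula for one sample or for paired data. Steps 2 to 4 nevertheless accept 14, to isolate the question of units.

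**2. Converting to patients per arm.** The sized contrast needs 14 + 14 = 28 surgical patients who are either frontal or temporal. If the rarer of those two sites has share s of Group A, the arm needs about 14/s evaluable patients for the expected count at that site to reach 14:

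| s | 14/s | 50 × s | 30 × s |
|---|---|---|---|
| 1/3 | 42 | 16.7 | 10 |
| 0.28 | 50 | 14 | 8.4 |
| 0.25 | 56 | 12.5 | 7.5 |
| 0.20 | 70 | 10 | 6 |

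The 30 kept as the maximum is enough on average only if s is at least 14/30 = 0.47, that is, with almost no occipital patients. Fifty is enough on average if s is at least 0.28.

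**3. Chance variation.** With no quota, the site counts are random. Treating them as multinomial, the probability that frontal and temporal both reach 14 is:

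| Frontal/temporal/occipital | 50 evaluable | 40 evaluable | 30 evaluable |
|---|---|---|---|
| 60/20/20 | 11% | 2% | <1% |
| 50/25/25 | 36% | 9% | <1% |
| equal thirds | 66% | 14% | <1% |
| 40/40/20 | 94% | 58% | <1% |

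The 30-patient column is relevant because III.b treats 30 evaluable per arm as sufficient. Going from 30 to 50 leaves room for 1 − 30/50 = 40% loss, although the plan does not predict that loss.

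**4. Patients with several sites.** They raise the raw count per site, but the site groups then overlap and are no longer independent. They lower the count of patients who belong to one site only. The plan has no rule for assigning them.

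**5. Separate matter: the 14 itself.** Frontal and temporal patients are independent groups. The two-sample normal formula on the same inputs gives 2 × 13.95 = 27.9, or 28 per site. With 14 per site, a two-sided two-sample t-test with difference 7.5 and SD 10 has about 48% power; with 10 per site, 36%. The drop from 80% to 48% comes from how 14 was computed. Falling short of 14 comes on top of that.

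**The case against.** The strongest reply is that 50 patients can be enough. With equal thirds the average is 16.7 per site, above 14, and a mix favouring frontal and temporal gives both sites 14 in 94% of cases if all 50 are evaluable. That stands: the plan does not make the site comparison impossible, and it would be wrong to say that it cannot be met.

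A reader might infer that the true requirement is 14 × 3 = 42 and that, by the plan's own rule, the site method is flatly the largest of the three. The documents do not support that. The only contrast sized is frontal versus temporal, which needs 28 patients, fewer than 30. No calculation asks for 14 occipital patients. The 42 follows only from an equal three-way mix, which the plan does not state.

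It can also be said that no trigger-site test is planned. Protocol III.d and III.g list comparisons within and between Groups A and B, and the SAP models treatment and time; site in the SAP means study centre. That limits the harm to a later, unplanned comparison. It does not remove the sizing claim in III.b.

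Finally, evidence that multi-site patients are expected is thin. The Background sentence "Factors predicting failure of surgery include excessive operative blood loss, and surgery on only one or two trigger sites" reports an earlier study's findings, not this trial's case mix. Only the wording in III.c that allows several sites bears directly on this trial.

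**Conclusion.** The mismatch of units is plain from III.b and does not depend on any assumption: 14 is per trigger site among operated patients, 30 and 16 are per arm, and the maximum is taken without conversion. The consequence is that 50 enrolled surgical patients may not secure 14 frontal and 14 temporal.

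How likely a shortfall is cannot be fixed from the documents. It rests on an assumed site mix, one site per patient, and an assumed number evaluable, and over those ranges the answer moves from very probable success to almost certain failure. Reading the plan as definitely failing the site comparison would go too far; so would attributing most of the lost power to the units, since even a full 14 per site falls well short of 80%. The main comparison of surgery with botulinum toxin is not affected by this point.

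**What to change.** In Protocol III.b:

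- State for each calculation whether its unit is patients per treatment arm or surgical patients per trigger site.
- Give the site requirement as a per-arm number, 14/s, with the assumed site mix and drop-out shown. If the 14 is itself corrected, carry the corrected figure through the same conversion.
- Remove the implication that 50 per arm gives 80% power for the site comparison.
- Label success by trigger site as exploratory.

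In Protocol III.g and the SAP, add one model fitted to Group A with an indicator for each site, reported as estimates with confidence intervals, so that patients with several sites are kept and not forced into one group. Treatment success must be defined first, since the documents give no definition of it.

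The cost is wording and one added analysis. The site comparison becomes estimation only. No extra patients are needed.

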Our goals in this study are:

- 1. To evaluate the effectiveness of surgical decompression in migraine headaches prospectively, using validated instruments, and to compare it to the effectiveness of a botulinum toxin injection protocol
 - a. Our hypothesis is that migraine surgery decreases the frequency and severity of migraine headaches significantly, as measured by

validated questionnaires, and that the reduction is greater and more sustainable than that seen with a botulinum toxin injection protocol

- 2. To determine which types of migraine headaches benefit most from surgical decompression and/or botulinum toxin injection
- 3. To identify prognostic factors for the success or failure of surgical decompression in migraine headache
 - a. These have been demonstrated in a previous study,⁹ but have not evaluated in a multi-center fashion.
- 4. To compare the long-term direct and indirect costs in patients with migraine headaches undergoing botulinum toxin A injections versus surgical decompression
 - a. We hypothesize that, over the long-term, surgical decompression is more cost-efficient than a botulinum toxin injection protocol

III. Procedures

a. Research design

This is a **prospective, multi-center** evaluation of the short, medium and long-term efficacy of surgical decompression in migraine headaches, comparing it to the efficacy of a botulinum toxin injection protocol.

b. Sample

Inclusion criteria:

-Patients with migraines related to a trigger site at the location of a branch of a cranial nerve (frontal, temporal, occipital)

-Patients with chronic migraine (≥15 days per month) as dictated by the FDA indication for botulinum, and as diagnosed by a board-certified neurologist

Exclusion criteria:

-Patients deemed by the senior author or the neurologist to not have migraine headaches, but an alternative diagnosis

-Patients with systemic conditions that make them poor candidates for surgery (coronary artery disease, uncontrolled diabetes mellitus, etc...)

-Patients with migraines related to inferior turbinate hypertrophy or septal deviation -Patients with a frontal, temporal or occipital trigger point who do not respond to a diagnostic botulinum toxin injection

-Hypersensitivity to any botulinum toxin preparation or to any of the components in the formulation

-Infection at the proposed injection site for botulinum

Sample size (power analysis)

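### No complication, reoperation or injection reaction is a specified measurement or outcome, and the 2-month, migraine-only log leaves treatment-complication costs out of the cost comparison

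*Protocol*

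**What the plan says.** Protocol section II (Objectives), item 4, sets out to compare long-term costs, direct as well as indirect, between injections and surgery, and hypothesises that surgery is the more cost-efficient.

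Protocol section III.c gives both groups the same post-treatment log. Besides migraine medication it records "2) physician visits for migraines, 3) ER visits for migraines". Missed work and any further expenses count only where migraine is the cause, and the log is limited to 2 months. The enrolment log has the same content and length. At 1, 2 and 2.5 years the patients complete three migraine-specific questionnaires (MWPLQ, MIDAS, MSQ).

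On clinical contact, section III.c says of the surgical group: "Those patients will be followed postoperatively". For each group it adds: "They will also be examined by a board-certified neurologist at 1 year postoperatively". It names nothing to be recorded at either contact. Section III.e states that "all assessment will be made by the patients themselves, without influence by the experimenters".

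Section III.d lists five measurements: headache count; "Cost of migraine-related medications, physician visits, ER visits"; the cost of work days lost to migraine; the MIDAS score; and the MSQ scores. The SAP (Outcomes) models MHI, three MIDAS scores, an MSQ sum and an MWPLQ total.

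**The concern.** An operation is being compared with repeated injections. Each can cause problems of its own, and those problems cost money. If the data collection admits only migraine-related events, a wound problem, a nerve deficit or an injection reaction cannot enter the comparison, however carefully the plan is followed.

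Two things are at stake. First, the study could report one treatment as better or cheaper with no harm counted against either. Second, objective 4 promises direct costs, and the cost of treating a complication is one of them. Section III.e says the placebo effect does not threaten the cost data. That does not protect those data from incomplete capture.

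**Working it through.** **Step 1: trace example events through the plan.** The events are illustrations; the documents do not list them.

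| Event | Post-treatment log (III.c) | Measurements (III.d) | SAP outcomes |
|---|---|---|---|
| ER visit for a wound problem, month 1 | Excluded: not for migraine | No | No |
| Physician visit for an injection reaction, month 1 | Excluded: not for migraine | No | No |
| Repeat decompression for persisting migraine, within the 2 months | Could be entered under other migraine-related costs | That log item is not carried forward | No |
| The same reoperation, month 14 | No log running | No | No |
| New sensory finding at the 1-year examination | Not a log item | No | No |

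The first two rows are lost by the wording of the log. The third can be logged but then has no place in the listed measurements. The fourth is lost to the time window: 2 of 30 months, or 6.7% of the 2.5-year follow-up. The last is lost because nothing from the examination feeds a measurement. In III.d one could read the migraine qualifier as applying to medications only. The visits come from the log, however, and the log restricts them to migraine.

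**Step 2: reproduce the plan's cost figures** (III.b, Sample size).
- Injection cost per year: 75 Units x 4 x $12 = $3,600; 75 x 4 x $15 = $4,500. Both match.
- Time to equal cost: $8,378 / $4,500 = 1.86 years; $8,378 / $3,600 = 2.33 years. The plan gives 1.9 to 2.3.
- Injection cost over 2.5 years at the mid-price: 2.5 x $4,050 = $10,125. This matches.

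**Step 3: planning margin for surgery at 2.5 years** (injection cost minus $8,378).
- $12 per Unit: 2.5 x $3,600 - $8,378 = $9,000 - $8,378 = $622.
- Mid-price: $10,125 - $8,378 = $1,747.
- $15 per Unit: 2.5 x $4,500 - $8,378 = $11,250 - $8,378 = $2,872.

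**Step 4: reoperation rate that removes each margin.** The rate is the margin divided by the cost of a reoperation. The documents give neither a rate nor a reoperation cost. Assume the full $8,378, and half of it ($4,189) to show the range, with no offsetting harm cost in the injection group.

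| Drug price | Margin | Rate at $8,378 | Rate at $4,189 |
|---|---|---|---|
| $12 per Unit | $622 | 7.4% | 14.8% |
| Mid-price | $1,747 | 20.9% | 41.7% |
| $15 per Unit | $2,872 | 34.3% | 68.6% |

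**Step 5: what recording would give with 50 per group.** With zero events, the exact two-sided 95% upper limit is 1 - 0.025^(1/50) = 7.1%. The chance of seeing at least one event is 1 - 0.95^50 = 92.3% if the true rate is 5%, and 1 - 0.99^50 = 39.5% if it is 1%. The study could therefore say something useful about common harms and little about rare ones. As planned, it can give no limit at all.

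**The case against.** **Routine care.** Section III.c says both treatments are routine care and that only the surveys and diaries are research procedures. The protocol sets no safety objective, and complications may well be in the clinical charts. Some pages were not available for this review. All of this stands as context, and the point is limited to the text supplied. It does not answer the gap: the available measurement, analysis and SAP sections plan no extraction from charts, and the study's purpose is to compare the two treatments.

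**Clinical contact.** A reader might infer that patients are hardly seen after treatment. The documents do not support that. Surgical patients are followed after the operation, the sample-size section assumes injections every 3 months, and a neurologist sees both groups at 1 year. The gap is that no harm data are specified from these contacts.

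**Reoperations.** A reader might infer that every reoperation is excluded by rule. That is too strong. A repeat operation for persisting migraine is arguably a migraine-related cost and could be logged, though only within the 2 months and under an item missing from section III.d.

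**Named risks.** A reader might infer that the protocol names complications and then fails to follow them. It does not. "Factors predicting failure of surgery include excessive operative blood loss" is a statement about prognosis, and "Infection at the proposed injection site for botulinum" is an exclusion criterion applied before treatment.

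**Indirect capture.** The questionnaires might register some harm through lost work or poorer quality of life. They are migraine-specific, however, and cannot identify or count a complication.

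**Conclusion.** The point holds as an omission, and it needs no assumed rate. Treatment-complication visits and costs are shut out by the log's own wording. Reoperations for migraine after the 2 months are not captured. No complication, reoperation or injection reaction is a listed measurement or modelled outcome. The cost comparison in objective 4 is therefore incomplete, and no harm rate can be stated for either group.

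Its effect on the cost result is unknown. The break-even rates are sensitivity figures only. They rest on an assumed reoperation cost and on margins built for sample-size planning, not on a measured result: section III.d does not list the cost of the operation, and the SAP models no dollar cost. A reader might infer that counting harm would overturn a cost advantage for surgery, or that the omission favours surgery. The documents support neither, because harms and their costs are missing in both groups.

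The change should be made because it is cheap and the missing information cannot be recovered reliably afterwards.

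**What to change.** 1. Leave the migraine-related log items as they are, at enrolment and after treatment. Rewording them only after treatment would break the before/after comparisons in sections III.d and III.g.
2. Add a separate item to the post-treatment log of both groups: visits, lost work days and costs for any problem following the surgery or injection.
3. Add a short checklist of complications and repeat operations, with date and reason, to the 1-, 2- and 2.5-year survey packets. It must be a new page, because the three questionnaires contain no visit log to adapt.
4. Record new findings on a form at the 1-year neurologist examination already planned. State its time origin for Group B, where the text counts from an operation that is not that group's study treatment. The start of the injection protocol already anchors that group's questionnaires and would serve.
5. Add complications and reoperations by group, with exact 95% confidence intervals, to section III.d and the SAP. Include their cost in the cost comparison, which also needs a place in the SAP.

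The cost is a few survey items, one form and a short amendment to both documents. It needs no new visits and no larger sample. The downsides are slightly longer surveys, some recall error in events reported a year or so later, and the possibility that either treatment looks less favourable on cost.
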